3.4.2 Secondary Endpoints [analyzed at year 1, 2, 3 unless otherwise stated]

- Proportion of patients with low level viremia, defined as a VL measurement >50 - <200 c/ml
- Proportion of patients with VL >50 c/ml with emergent resistance mutations (if available)
- Proportion of patients with virologic rebound, defined as two consecutive VL measurements \geq 200 c/ml
- Proportion of patients with two consecutive measurements of \geq 200 c/ml, or treatment switch due to VF or due to intolerance as determined at the discretion of the physician
- Proportion of patients VL <50 c/ml
- Number of monitoring measures [normalized to patient years]
- Number and frequency of serious adverse events (SAEs) [normalized to patient years]
- Number and frequency of adverse drug reactions (ADRs) [normalized to patient years]
- Adherence to therapy [refers to missed monthly doses]
- Change in lipid laboratory values

- Change in treatment satisfaction [HIV Treatment Satisfaction questionnaire]
- Change in symptom distress [HIV Symptom Distress Module questionnaire]
- Reason for switch to Juluca

[* Any subsequent measurement will be accepted as a consecutive measurement as long as measured no later than 120 days after the initial measurement. If no subsequent VL measurement is performed within 120 days this is scored as a confirmed VL.]

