### 6.2 Secondary Objectives

- Gain an understanding of the major relevant patient populations for JULUCA in Germany, in terms of patient characteristics and history
- Describe real-life efficacy profile of JULUCA
- Describe real-life tolerability profile of JULUCA as measured by discontinuation rates due to adverse drug reactions (ADRs) and overall number of serious adverse events (SAEs)
- Analyze the development of viral resistance by evaluating available resistance data in case of virologic failure
- Describe impact on lipid metabolism
- Evaluate medical need for a substance and/or class sparing treatment regimen by assessing the reason for switching to JULUCA
- Describe participants' treatment satisfaction and symptom distress based on validated questionnaires
- Evaluate number of monitoring measures and referrals to other specialists

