# 11 Planned Analyses

The CSR is planned to comprise the baseline characteristics, all primary and secondary endpoints (see chapters 11.3 and 11.3.2 respectively) as well as other relevant variables as described below.

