### 11.3.2 Secondary Endpoints (EPs) (analyzed at years 1, 2 and 3 follow-up, unless otherwise stated)

- Primary endpoint is the proportion of participants with sustained virologic suppression, defined as HIV-RNA <50 copies/mL or if between 50-200 copies/mL with a subsequent next available measurement\* (within 120 days) <50 copies/mL at years 1 and 2 follow-up
- Proportion of participants with HIV-RNA <50 copies/mL at years 1, 2 and 3 follow-up
- Proportion of participants with low level viremia, defined as a HIV-RNA measurement ≥50 copies/mL and <200 copies/mL at years 1, 2 and 3 follow-up
- Proportion of participants with virologic rebound, defined as two consecutive HIV-RNA measurements ≥200 copies/mL from baseline until year 3 follow-up
- Proportion of participants with two consecutive measurements of ≥200 copies/mL, or treatment switch due to virologic failure or due to intolerance as determined at the discretion of the physician from baseline until year 3 follow-up
- Number of HIV monitoring measures (HIV-RNA measurements) [normalized to participant years] from baseline until year 3 follow-up
- Number and frequency of serious adverse events (SAEs) from baseline until year 3 follow-up [normalized to participant years] (see 11.3.10)
- Number and frequency of adverse drug reactions (ADRs) from baseline until year 3 follow-up [normalized to participant years] (see 11.3.10)
- Adherence to therapy [refers to missed monthly doses] at years 1, 2 and 3 follow-up (see 11.3.4)
- Change in lipid laboratory values at years 1, 2 and 3 follow-up (see 11.3.8.3)
- Change in treatment satisfaction [HIV Treatment Satisfaction questionnaire] at years 1, 2 and 3 follow-up (see 11.3.12.2)
- Change in symptom distress [HIV Symptom Distress Module questionnaire] at years 1, 2 and 3 follow-up (see 11.3.12.1)
- Reason for switch to DTG+RPV (see 11.3.5)
- Referral to other medical specialist from baseline until year 3 follow-up (see 11.3.7)
- Proportion of participants with resistance testing from baseline until year 3 follow-up
- Listing of detected resistance-associated mutations from baseline until year 3 follow-up
  - Listing of new (emerging) resistance-associated mutations, incl. resistance-associated mutations detected prior to treatment with DTG+RPV and last HIV-RNA

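### SAP 11.3.2 omits the protocol's secondary endpoint on viremia with emergent resistance and plans a cumulative testing share and listings instead

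*SAP*

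**What the plan says.** Protocol 3.4.2 includes among its secondary endpoints "Proportion of patients with VL >50 c/ml with emergent resistance mutations (if available"). The section heading sets the timing: "Secondary Endpoints [analyzed at year 1, 2, 3 unless otherwise stated". No denominator is given.

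SAP 6.2 keeps the matching objective: "Analyze the development of viral resistance by evaluating available resistance data in case of virologic failure".

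SAP 11.3.2 contains no such proportion. Its resistance items are:

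- "Proportion of participants with resistance testing from baseline until year 3 follow-up"
- "Listing of detected resistance-associated mutations from baseline until year 3 follow-up"
- nested under the second item, "Listing of new (emerging) resistance-associated mutations, incl. resistance-associated mutations detected prior to treatment with DTG+RPV and last HIV-RNA"

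The only other resistance output in the SAP is the baseline listing of mutations found before DTG+RPV (SAP 11.2.3). SAP section 11 states: "The CSR is planned to comprise the baseline characteristics, all primary and secondary endpoints". The SAP's Summary of Changes mentions only stratification variables and the HIVTSQs analysis.

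**The concern.** A prespecified endpoint has been replaced by different outputs, and nothing in the SAP says so. For a two-drug maintenance regimen, resistance emerging during viremia is a result that readers will look for, and this is the only protocol endpoint that serves the resistance objective.

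To interpret an emergent-mutation count, a reader needs to know how many participants were viremic on treatment and how many of those were tested. In routine care, testing is at the physician's discretion and may be sparse. No planned output links testing to viremia. If the SAP is followed as written, the study report will omit the protocol proportion, and its denominator will be left for readers to choose.

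**Working it through.** **Any stated figure.** The documents give no figure for this endpoint. Their only sample-size figure concerns the primary endpoint, and it reproduces: an exact 95% interval at 90% has width 0.0997 with n = 158, and 158 / (1 − 0.30) = 225.7, rounded up to 226. Nothing below depends on it.

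**Step 1: compare the endpoint lists.** Protocol 3.4.2 has 13 secondary endpoints. Twelve reappear in SAP 11.3.2, some with changed timing. The thirteenth, viremia with emergent resistance, does not.

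**Step 2: ask what the planned outputs can supply.**

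| Element needed | Available from the SAP's outputs? |
|---|---|
| Number with emergent mutations | Yes, by counting the emergent-mutation listing |
| Restriction to VL >50 | Approximately. The listing shows last HIV-RNA, which is not tied to the resistance sample, and no test date is specified |
| All participants as denominator | Yes, from the mFAS size (SAP 10.4) |
| Tested participants as denominator | Partly. The share runs from baseline, and the flow chart (SAP 7.4) places resistance testing at the baseline visit, before therapy starts, so pre-treatment tests may be counted |
| Participants with VL >50 as denominator | Only as yearly snapshots, from the complement of "Proportion of participants with HIV-RNA <50 copies/mL at years 1, 2 and 3 follow-up". That gives ≥50 rather than >50, in the assessment closest to each anniversary while on treatment and on study (SAP 10.2). Viremia between windows, or before leaving the study, is missed |
| Testing rate among viremic participants | No |
| Results at years 1, 2 and 3 | No; all three items are cumulative |

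Virologic rebound is cumulative to year 3 in SAP 11.3.2, but it requires two consecutive values ≥200 and is not crossed with testing.

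**Step 3: effect of the denominator (assumed counts).** Proportion = k / N, where k is the number with emergent mutations. Take N = 250 (recruitment target), N = 0.10 × 250 = 25 (not suppressed under the 90% efficacy assumption) and N = 10 tested (assumed).

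| k | of 250 | of 25 | of 10 |
|---|---|---|---|
| 1 | 0.4% | 4.0% | 10% |
| 2 | 0.8% | 8.0% | 20% |
| 3 | 1.2% | 12.0% | 30% |

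For any k, the second column is 250 / 25 = 10 times the first, and the third is 250 / 10 = 25 times the first.

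**Step 4: why the overall testing share does not settle it.** Keep k = 2, both viremic, with 10 tested overall and 25 viremic. The SAP would report 10 / 250 = 4% tested. The number of viremic participants tested on treatment could be anything from 2 (only the two cases) to 10. Testing among the viremic would then lie between 2 / 25 = 8% and 10 / 25 = 40%, and emergent resistance among the viremic and tested between 2 / 10 = 20% and 2 / 2 = 100%. The planned tables could not narrow these ranges.

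**The case against.** The strongest reply is that little is lost:

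- The testing share and listings carry much of the information. Tested participants minus those listed gives tested without mutations, so untested and tested-negative participants can be told apart across the whole cohort.
- The emergent-mutation listing shows last HIV-RNA.
- The objective refers to virologic failure, and the SAP counts rebound, and a composite that includes switch for virologic failure, cumulatively to year 3. It also lists last HIV-RNA for discontinuations for virologic reasons (SAP 11.3.5).
- With few events, a participant-level listing may tell more than a percentage.
- The missing denominator is a gap in the protocol, not one that the SAP created.
- The statement in SAP section 11 about reporting all endpoints cross-refers to the SAP's own list.

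Most of this stands. It rules out three stronger inferences a reader might draw: that the proportion cannot be recovered at all, that absence of resistance cannot be distinguished from absence of testing, and that the resistance objective goes unanswered. An approximate cumulative figure can be hand-counted, the cohort-level distinction is broadly available subject to the baseline-test ambiguity, and failure itself is counted.

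The reply does not cover the omission, the absence of any link between testing and viremia, or the lost yearly results. The undefined denominator makes it more necessary for the SAP to choose one.

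**Conclusion.** The point holds as an unrecorded departure from the protocol in one descriptive secondary endpoint. The planned outputs allow an approximate cumulative proportion of all or of tested participants. They do not give the proportion among participants with VL >50, the testing rate in that group, or results at years 1, 2 and 3.

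The gap is in the planned analysis, not in the data: the SAP flow chart shows resistance testing at baseline, follow-up and discontinuation, and HIV-related laboratory values reported continuously. The primary endpoint is unaffected. The tenfold and twenty-five-fold differences rest on assumed counts and show sensitivity to the denominator; they do not predict the study's result. The change is worth making before analysis, because it is cheap and the denominator is best fixed before the cases are seen.

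**What to change.** Restore the endpoint in SAP 11.3.2 and define it:

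- **Numerator:** participants with an emergent mutation and a VL >50 c/ml linked to the resistance test.
- **Denominator:** stated explicitly, since the protocol gives none. Participants with on-treatment VL >50 is the natural choice, with the number tested shown beside it.
- **Table:** number with on-treatment VL >50, number of those tested on treatment, and number with emergent mutations, at years 1, 2 and 3 and cumulatively to year 3.
- **Listings:** keep them.

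If the sponsor prefers the current outputs, record the change from the protocol in the SAP with a reason. Confidence intervals and a further tier for confirmed values ≥200 are optional in a descriptive study. The cost is one small descriptive table from data already collected, with no new assessments.

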### 11.3.3 Immunologic response at years 1, 2 and 3 follow-up

- Absolute CD4 cell count [cells/ $\mu$ L]
- Change in absolute CD4 cell count [cells/ $\mu$ L] from baseline; comparison of levels within groups (paired observations, Wilcoxon signed rank test)
- Proportion of participants with absolute CD4 cell counts <200/ $\mu$ L; 200-349/ $\mu$ L; 350-499/ $\mu$ L;  $\geq$  500/ $\mu$ L (calculated)
- Absolute CD8 cell count [cells/ $\mu$ L]
- Change in absolute CD8 cell count [cells/ $\mu$ L] from baseline; comparison of levels within groups (paired observations, Wilcoxon signed rank test)
- CD4/CD8 ratio (calculated)
- Change in CD4/CD8 ratio (calculated) from baseline
- Proportion of participants with CD4/CD8 ratio <1 vs  $\geq$ 1 (calculated)
- Change in proportion of participants with CD4/CD8 ratio <1 vs  $\geq$ 1 (calculated) from baseline

### 11.3.4 Participant self-assessment of adherence at years 1, 2 and 3 follow-up

- Participant self-assessment of adherence of last months (i.e. missed doses) (N, %)

### 11.3.5 Study discontinuation prior to year 3 follow-up

- Proportion of participants discontinued the JUNGLE study prior to year 3 follow-up visit
- Reasons for study discontinuation (N, %) - incl. listing of 'other' reason
- Participants discontinued due to virologic reasons: LOCF HIV-RNA copies/mL (listing)
- ART regimes after discontinuation of the JUNGLE study (N, %)

### 11.3.6 Incident comorbidities and new comedications

- Proportion of participants with a new (incident) diagnosis of the relevant comorbidity-classes (all observations from baseline until year 3 follow-up)
- Proportion of participants treated with a new (incident) relevant comedication-classes (all observations from baseline until year 3 follow-up)

### 11.3.7 Referrals to another medical specialists

- Percentage of participants referred to another medical specialists (all referrals from baseline until year 3 follow-up)

### 11.3.8 Laboratory parameters at years 1, 2 and 3 follow-up

#### 11.3.8.1 Renal parameters at years 1, 2 and 3 follow-up

- Serum creatinine [mg/dL]
- Change in serum creatinine [mg/dL] from baseline
- eGFR [mL/min/1.73 m^2] (calculated)

### CKD-EPI Creatinine Equation (2021)

$$eGFR_{cr} = 142 \times \min(S_{cr}/\kappa, 1)^\alpha \times \max(S_{cr}/\kappa, 1)^{-1.200} \times 0.9938^{\text{Age}} \times 1.012 \text{ [if female]}$$

( $Scr$  = standardized serum creatinine in mg/dL;  $\kappa$  = 0.7 (females) or 0.9 (males);  $\alpha$  = -0.241 (female) or -0.302 (male);  $\min(Scr/\kappa, 1)$  is the minimum of  $Scr/\kappa$  or 1.0;  $\max(Scr/\kappa, 1)$  is the maximum of  $Scr/\kappa$  or 1.0; Age (years))

- Change in eGFR [mL/min/1.73 m^2] from baseline
- Blood nitrogen urea [mg/dL]
- Change in blood nitrogen urea [mg/dL] from baseline

#### 11.3.8.2 Liver parameters at years 1, 2 and 3 follow-up

- ALT [U/L]
- Change in ALT [U/L] from baseline
- AST [U/I]
- Change in AST [U/I] from baseline
- Gamma-GT [U/L]
- Change in gamma-GT [U/L] from baseline
- Total bilirubin [mg/dL]
- Change in total bilirubin [mg/dL] from baseline
- Bilirubin, direct [mg/dL]
- Change in bilirubin, direct [mg/dL] from baseline
- Alkaline phosphatase [U/L]
- Change in alkaline phosphatase [U/L] from baseline

#### 11.3.8.3 Lipids at years 1, 2 and 3 follow-up

- Total cholesterol [mg/dL]
- Change in total cholesterol [mg/dL] from baseline
- LDL cholesterol [mg/dL]
- Change in LDL cholesterol [mg/dL] from baseline
- HDL cholesterol [mg/dL]
- Change in HDL cholesterol [mg/dL] from baseline
- Triglycerides [mg/dL]
- Change in triglycerides [mg/dL] from baseline

#### 11.3.8.4 Blood count at years 1, 2 and 3 follow-up

- Hemoglobin [g/dL]
- Change in hemoglobin [g/dL] from baseline
- Hematocrit [%]
- Change in hematocrit [%] from baseline
- Red blood cells (RBC, erythrocytes) [ $\times 10^6/\mu\text{L}$  (T/L)]
- Change in red blood cells (RBC, erythrocytes) [ $\times 10^6/\mu\text{L}$  (T/L)] from baseline
- White blood cells (WBC, leukocytes) [ $\times 10^3/\mu\text{L}$  (G/L)]
- Change in white blood cells (WBC, leukocytes) [ $\times 10^3/\mu\text{L}$  (G/L)] from baseline
- Lymphocytes [%]
- Change in lymphocytes [%] from baseline
- Platelets [G/L]

- Change in platelets [G/L] from baseline

#### 11.3.8.5 Serum chemistry at years 1, 2 and 3 follow-up

- Amylase [U/L]
- Change in amylase [U/L] from baseline
- Lipase [U/L]
- Change in lipase [U/L] from baseline
- Lactate dehydrogenase (LDH) [U/L]
- Change in lactate dehydrogenase (LDH) [U/L] from baseline
- Creatinine kinase (CK) [U/L]
- Change in creatinine kinase (CK) [U/L]
- Serum glucose [mg/dL]
- Change in serum glucose [mg/dL] from baseline
- Uric acid [mg/dL]
- Change in uric acid [mg/dL]
- Serum albumin [mg/dL]
- Change in serum albumin [mg/dL] from baseline
- C reactive protein (CRP) [mg/dL]
- Quick [%]

#### 11.3.8.6 Urine chemistry at years 1, 2 and 3 follow-up

- Qualitative urine analysis (urine dipstick): leukocytes, pH value, proteins, bilirubin, urobilinogen, nitrite, glucose, ketones, and blood
- Quantitative urine analysis, displayed as listing:
  - Total protein [mg/L]
  - Albumin [mg/L]
  - Creatinine [g/L]
  - Phosphate [g/L]
  - Glucose [mg/L]
  - $\alpha$ -1-microglobuline [mg/L]

#### 11.3.9 Body weight and BMI at years 1, 2 and 3 follow-up

- Weight [kg]
- Change in weight [kg] from baseline;
- BMI [ $\text{kg}/\text{m}^2$ ] (calculated)
- Change in BMI [ $\text{kg}/\text{m}^2$ ] (calculated) from baseline

#### 11.3.10 (Serious) adverse drug reactions and serious adverse events from baseline until year 3 follow-up

Incident (serious) adverse drug reactions [(S)ADRs] and severe adverse events [SAEs] of each participant will be presented in listings and as

- Number and frequency of SAEs [normalized to patient years]
- Number and frequency of (S)ADRs [normalized to patient years]

For definition of periods see 10.2.1.

In detail the following parameters will be evaluated:

Include nature of the (S)ADR/SAE (MedDRA System Organ Class and MedDRA Preferred Term), date and time of onset and resolution, intensity, causal relationship with DTG+RPV, seriousness, interruption or withdrawal of DTG+RPV, countermeasure and outcome.

Handling of repeated events in the summary statistics:

- ‘per participant’: Each subject will only be counted once and any repetitions of (S)ADR/SAE will be ignored; the denominator will be the total population size.
- ‘per MedDRA term’: All MedDRA terms will be counted and the repetitions of (S)ADR/SAE will be not ignored; the denominator will be the total MedDRA term number.

#### **11.3.11        Pregnancies from baseline until year 3 follow-up**

- Listing of incident pregnancies

#### **11.3.12        HIV Symptoms Distress Module (SDM) and HIV Treatment Satisfaction Questionnaire (HIVTSQs) at years 1, 2 and 3 follow-up**

##### **11.3.12.1      HIV Symptoms Distress Module (SDM)**

Each of the following parameters of the SDM will be calculated as observed.

- SDM completed (yes/no)
- SDM total score
- Change in SDM total score from baseline

##### **11.3.12.2      HIV Treatment Satisfaction Questionnaire (HIVTSQs) at years 1, 2 and 3 follow-up**

The HIVTSQs total score will be calculated as described in section 10.3 and individual item scores will be calculated as observed.

- HIVTSQs completed (yes/no)
- HIVTSQs total score
- Change in HIVTSQs total score from baseline
- HIVTSQs individual item scores
- Change in HIVTSQs individual item scores from baseline

## **12    Software**

Data merge and statistical analyses will be carried out using the STATA® package (version Stata/SE 17).

## 13 Output Format

Tables and listings will be provided as Portable Document Format (PDF) or Microsoft Word (DOCX) file. Figures will be provided as Enhanced Meta File (EMF) and/or Portable Network Graphics (PNG) file.
